**Appendix 3**      **Criteria for Identifying ECG Measurements of Potential Clinical Relevance**

[figure not shown]
Variable	Criterion Value a	Change Relative to Baseline a
Rate		
Tachycardia	≥ 120 bpm	increase of ≥ 15 bpm
Bradycardia	≤ 50 bpm	decrease of ≥ 15 bpm
Rhythm		
Sinus tachycardia b	≥ 120 bpm	increase of ≥ 15 bpm
Sinus bradycardia c	≤ 50 bpm	decrease of ≥ 15 bpm
Supraventricular premature beat	all	not present → present
Ventricular premature beat	all	not present → present
Supraventricular tachycardia	all	not present → present
Ventricular tachycardia	all	not present → present
Atrial fibrillation	all	not present → present
Atrial flutter	all	not present → present
Conduction		
1° atrioventricular block	PR ≥ 200 msec	increase of ≥ 50 msec
2° atrioventricular block	all	not present → present
3° atrioventricular block	all	not present → present
Left bundle-branch block	all	not present → present
Right bundle-branch block	all	not present → present
Pre-excitation syndrome	all	not present → present
Other intraventricular conduction block d	QRS ≥ 120 msec	increase of ≥ 20 msec
Infarction		
Acute or subacute	all	not present → present
Old	all	not present → present ≥ 12 weeks post trial entry
ST/T Morphological		
Myocardial Ischemia	all	not present → present
Symmetrical T-wave inversion	all	not present → present
Increase in QTc	QTcF ≥ 450 msec (men) QTcF ≥ 470 msec (women)	

[figure not shown]
a In order to be identified as potentially clinically relevant, an on-treatment value must meet the “Criterion Value” and also represent a change from the subject’s baseline value of at least the magnitude shown in the “Change Relative to Baseline” column.

[figure not shown]
b No current diagnosis of supraventricular tachycardia, ventricular tachycardia, atrial fibrillation, atrial flutter, or other rhythm abnormality.

[figure not shown]
c No current diagnosis of atrial fibrillation, atrial flutter, or other rhythm abnormality.

[figure not shown]
d No current diagnosis of left bundle branch block or right bundle branch block.

[figure not shown]

This page is a manifestation of an electronically captured signature

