- Subjects who have received high-dose antipsychotics exceeding the equivalent of ≥ 3 mg of risperidone (eg, ≥ 5 mg of haloperidol, ≥ 375 mg quetiapine, ≥ 10 mg olanzapine, or local equivalent) within 90 days prior to screening.
- Subjects who have received multiple antipsychotic medications simultaneously for a period of > 7 days within 90 days prior to screening.
- Subjects with evidence of serious risk of suicide based on the Sheehan Suicidality Tracking Scale (Sheehan-STS), ie, a score of 3 or 4 on any one question 2 through 6 or 11, or a score of 2 or higher on any one questions 1a, 7 through 10, or 12, or who, in the opinion of the investigator, present a serious risk of suicide.
- Subjects considered in poor general health based on the investigator's judgment. Examples include subjects who have a recent clinically significant weight loss, chronic dehydration or hypovolemia, poor fluid or nutritional intake, or a recent clinically significant infection, as per the investigator's judgment.

Trial Site(s):

The trial is expected to enroll subjects at approximately 80 sites worldwide.

Investigational Medicinal Product(s), Dose, Dosage regimen, Treatment period, Formulation, Mode of Administration: The IMP will be supplied as brexpiprazole tablets or matching placebo tablets. Each dose will be supplied as blister cards containing sufficient tablets for 7 (+2) days. When accessed by the site, the eSource method will assign specific blister card number(s) to be dispensed to a subject.

After a 2- to 42-day screening period, eligible subjects will be randomized in a 2:1 ratio to brexpiprazole or placebo. Within the brexpiprazole arm, subjects will be further randomized in a 1:2 ratio to 2 mg/day or 3 mg/day.

The total duration of double-blind treatment will be 12 weeks for all randomized subjects.

Neither the investigator nor the subject will be aware of the treatment assignment. All doses of brexpiprazole and matching placebo will be taken orally once daily, preferably in the morning, and will be administered without regard to meals. Brexpiprazole (or matching placebo) should be taken at approximately the same time each day.

Trial Assessments:

Efficacy: CMAI, Clinical Global Impression Severity of Illness (CGI-S) scale, Clinical Global Impression Improvement of Illness (CGI-I) scale,

Pharmacokinetic (PK),

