1.3 Known and Potential Risks and Benefits

As of 30 Apr 2017, at least 8978 subjects have been exposed to a dose of brexpiprazole across the phase 2/3 completed trials for AAD, schizophrenia, MDD, ADHD, and PTSD, including 3249 subjects who have been exposed to brexpiprazole for at least 6 months and 1809 subjects who have been exposed for at least 1 year.

Data from clinical trials completed to date indicate that the maximum tolerated dose (MTD) of brexpiprazole in healthy adult subjects is 6 mg after single-dose administration and 2 mg after once-daily, multiple-dose (14 days) administration. The MTD of brexpiprazole in subjects with schizophrenia, MDD, or ADHD has not been established. Within the 3 indications with completed trials, data from completed multiple-dose phase 1 clinical trials indicate brexpiprazole is tolerated at multiple oral doses up to 12 mg/day in subjects with schizophrenia or schizoaffective disorder, up to 4 mg/day as adjunctive therapy in adult subjects with MDD or ADHD, and up to 3 mg/day as adjunctive therapy in elderly subjects (70 to 85 years of age) with MDD.

Preliminary data from the 2 completed phase 3 trials (Trials 331-12-283 and 331-12-284) in subjects with AAD indicate brexpiprazole is safe and well tolerated, with no new safety signals identified in this elderly population. There was a low incidence of treatment-emergent adverse events (TEAEs) associated with extrapyramidal symptoms (EPS) (5.8% brexpiprazole versus 4.0% placebo), weight increased (1.4% brexpiprazole versus 0.7% placebo), somnolence/sedation (3.7% brexpiprazole versus 2.2% placebo), falls (1.6% brexpiprazole versus 2.9% placebo), cardiovascular events (5.1% brexpiprazole versus 2.9% placebo), cerebrovascular events (0.7% brexpiprazole versus 0.4% placebo). Overall, the TEAEs associated with mortality do not appear to support a relationship with the IMP. Results from the 2 completed phase 3 trials in subjects with AAD (Trial 331-12-283 and

Trial 331-12-284) showed that brexpiprazole doses up to 2 mg/day are safe and well-tolerated in this population.

Please refer to the IB for a summary of available nonclinical and clinical safety data. 13

2 Trial Rationale and Objectives

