Assessment	Screening ^a	Baseline (Day 0)	Week 2 (±2 days)	Week 4 (±2 days)	Week 6 (±2 days)	Week 8 (±2 days)	Week 10 (±2 days)	Week 12 or ET ^b (±2 days)	Follow- up ^c (+2 days)	Week 16 ^d	Notes
Prolactin (blinded)	X							X			Section 3.7.5.2
TSH with reflex to free T ₄ if abnormal	X										Section 3.7.5.2
HbA _{1c}	X							X			Section 3.7.5.2
PT, aPTT, and INR	X							İ			Section 3.7.5.2
Urine pregnancy test (women of childbearing potential) only	X							X			Section 3.7.5.2
ECG	X	X				X		X			Section 3.7.5.4
Urine drug screen and blood alcohol test	X										Section 3.7.5.2 Section 4.2
MMSE	X	X						X			
Sheehan-STS	X	X						X			Section 3.7.5.5.4
Extrapyramidal symptoms scales (SAS, AIMS, BARS)		X						X			
Adverse events	X	X	X	X	X	X	X	X	X		Section 5
Pharmacokinetic sampling		X				X		X			Section 3.7.6.1.1
			I	I			I				
Concomitant medications	X	X	X	X	X	X	X	X	X		Section 3.7.4
Mortality status assessment										X	Section 3.7.1.5
OTHER PROCEDURES											
IMP dispensing		X	X	X	X	X	X				Section 8.4
IMP accountability		X	X	X	X	X	X	X			

aPTT = activated partial thromboplastin time; INR = International Normalized Ratio; PT = prothrombin time.

^aSee Section 3.7.1.1.

^bSee Section 3.1.

^cSee Section 3.8.3.2.

^dNote that this visit is 16 weeks postbaseline and only for subjects who terminate early from the trial.

^eIf a previous MRI or CT scan of the brain performed after the onset of symptoms of dementia is not available, then an MRI/CT scan of the brain should be performed during screening. In addition, a repeat MRI/CT scan of the brain may be requested to be performed by CST or the IAP in order to confirm eligibility.

^fIf a fasting blood sample was obtained at the screening visit and less than 14 days have elapsed since the screening visit, clinical laboratory tests (hematology, serum chemistry, and urinalysis) do not need to be repeated at the baseline visit.

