### 9.4 12-Lead ECG

Summary statistics for change from baseline in ECG parameters will be provided by treatment and by visit.

In addition, the incidence of treatment-emergent PCR values identified using prospectively defined criteria for ECG will be summarized by treatment group. Listing of PCRs by subject and by test will be provided.

For the analysis of QT and QTc, data from three consecutive complexes (representing three consecutive heart beats) will be measured to determine average values. The following QT corrections will be used for reporting purposes in the clinical study report:

- QTcB is the length of the QT interval corrected for heart rate by the Bazett formula:  $QTcB = QT / (RR)^{0.5}$
- QTcF is the length of the QT interval corrected for heart rate by the Fridericia formula:  $QTcF = QT / (RR)^{0.33}$
- QTcN is the length of the QT interval corrected for heart rate by the FDA Neuropharm Division formula:  $QTcN = QT / (RR)^{0.37}$

Categorical changes in ECG parameters during the double-blind treatment period will be summarized based on the criteria in [Table 9.4-1](#).

Table 9.4-1 Categorical Change Criteria in QT/QTc Parameters		
Classification	Category	Criteria
QT	New onset ( $\geq 450$ msec for men or $\geq 470$ msec for women)	New onset in QT means a subject who attains a cut off value during treatment period but not at baseline.
QTc a	New onset ( $\geq 450$ msec for men or $\geq 470$ msec for women)	New onset in QTc means a subject who attains a cut-off value during treatment period but not at baseline.
	New onset ( $\geq 450$ msec for men or $\geq 470$ msec for women) and $> 10\%$ increase	New onset and $> 10\%$ increase in QTc means a subject who attains a cut off value and $> 10\%$ increase during treatment period but not at baseline
	New onset ( $> 500$ msec)	New onset ( $> 500$ msec) in QTc means a subject who attains a value $> 500$ msec during treatment period but not at baseline.
	Increase 30 - 60 msec	Increase from baseline value $> 30$ and $\leq 60$ msec in QTc
	Increase $> 60$ msec	Increase from baseline value $> 60$ msec in QTc

a QTc categorical change criteria apply to QTcB, QTcF and QTcN.

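### The ECG flag for a new old infarction requires 12 weeks since an undefined trial entry in a trial with 12 weeks of treatment, so some subjects, mainly early terminators, cannot be counted

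*SAP*

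**What the plan says.** In SAP Appendix 3, the Old row under Infarction accepts any value as the criterion and gives the change condition as "not present → present ≥ 12 weeks post trial entry". Protocol Appendix 4 has the same row, with the same time condition, "≥ 12 weeks post trial entry". Footnote a of the SAP table begins "In order to be identified as potentially clinically relevant, an on-treatment value must meet the" criterion value, and it goes on to require the stated change from the subject's baseline as well. Both columns must therefore be satisfied.

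SAP Section 9.4 uses these flags in a by-arm summary: "the incidence of treatment-emergent PCR values identified using prospectively defined criteria for ECG will be summarized by treatment group". A listing by subject accompanies it.

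The protocol synopsis states: "The total duration of double-blind treatment will be 12 weeks for all randomized subjects". Protocol Table 3.7-1 schedules ECGs at screening, baseline, Week 8 and Week 12 or ET, with ±2 days at the post-baseline visits and none at follow-up. Protocol Section 3.7.5.4 asks for an ECG whenever a subject terminates early.

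Neither document defines trial entry. Protocol Section 3.4.1.1 links the term to the giving of assent, which points to the consent stage.

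**The concern.** A waiting period as long as the whole treatment period leaves almost no on-treatment time in which the flag can be raised. No other row in the table that asks for a finding to go from absent to present has a time condition, and that includes acute or subacute infarction.

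The subjects at risk of being missed are not a random subset. They are mainly those who stop early, who are meant to have an ECG when they stop. If early termination differs between arms, the chance of being counted differs between arms too. Because trial entry is undefined, two programmers could also produce different tables from the same data.

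**Working it through.** The plan gives no figure of its own to reproduce, so the check is day arithmetic.

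**Inputs**
- Waiting period: 12 weeks = 12 × 7 = 84 days (SAP Appendix 3).
- Baseline is Day 0 and the first dose is on Day 1 (Protocol Section 3.2, Table 3.7-1).
- Week 8 window: 56 ± 2 = Days 54 to 58. Week 12 window: 84 ± 2 = Days 82 to 86 (Table 3.7-1).
- Screening length *s*: 2 to 42 days, extendable with medical monitor approval (Protocol Section 3.1).

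**Rule tested.** An ECG on Day *d* can be flagged only if the days from entry to *d* are at least 84.

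| Meaning of trial entry | Week 8 (Days 54–58) | ET | Week 12 (Days 82–86) |
|---|---|---|---|
| Baseline, Day 0: *d* ≥ 84 | never | not before Day 84 | Days 84, 85, 86 only (3 of 5) |
| First dose, Day 1: *d* − 1 ≥ 84 | never | not before Day 85 | Days 85, 86 only (2 of 5) |
| Consent: *s* + *d* ≥ 84 | only if *s* is long enough | from Day 84 − *s* | always |

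**Consent reading in detail**
- Week 8 on Day 54 needs *s* ≥ 84 − 54 = 30 days. Day 56 needs 28 days, and Day 58 needs 26 days.
- The earliest ET ECG that can count is on Day 84 − 2 = 82 after a 2-day screening, Day 84 − 30 = 54 after 30 days, and Day 84 − 42 = 42 after 42 days.
- Week 12 falls between 82 + 2 = 84 and 86 + 42 = 128 days after consent, so it always qualifies.
- As an illustration only, assume that screening length is spread evenly over whole days. A Day 56 ECG then qualifies for 3 of the 29 lengths from 2 to 30 days (about 10%), or 15 of the 41 lengths from 2 to 42 days (about 37%). The documents do not give the actual distribution.

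**From ECGs to subjects.** The table in SAP Section 9.4 is an incidence, and footnote a compares each value with baseline, not with the previous visit. A pattern absent at baseline, first seen at Week 8 and still present at Week 12 therefore meets the rule at Week 12. It qualifies under the consent reading always, under the baseline reading if the Week 12 ECG is on Day 84 or later, and under the first-dose reading if it is on Day 85 or later. The subjects who are lost are:
1. those whose last ECG is an ET recording too early to reach 84 days from entry;
2. under the baseline or first-dose reading, those whose Week 12 ECG is in window but too early (Days 82–83, or 82–84);
3. those whose pattern is read at Week 8 but no longer at Week 12.

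**The case against.** The best defence is that for most subjects the flag is delayed, not lost. This stands. A reader might infer that every old infarction first seen at Week 8 goes uncounted, but comparison with baseline means a completer with a persistent pattern is normally counted at Week 12.

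Second, the protocol's own use of trial entry points to consent. On that reading the Day 82–83 gap disappears and some ET ECGs qualify. This also stands, but the term remains undefined for this table, and the flag then depends on screening length, which has no bearing on whether a finding is new.

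Third, the time limit may be deliberate, because an old pattern seen soon after entry could predate treatment. That is plausible, but the documents do not say so. The row already requires absence at baseline, and Protocol Section 3.7.5.4 has every ECG read by a central service.

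Fourth, other routes catch cardiac events. Acute or subacute infarction, ischemia, T-wave inversion and left bundle-branch block are flagged without a time limit. The investigator reviews every ECG, and SAP Section 9.1 summarises serious adverse events and those leading to discontinuation by arm. This stands and limits the harm, although it does not repair the planned count.

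Two further inferences fail. Applying the 12–13% dropout in SAP Section 4 to 330 subjects gives 330 × 0.12 = 39.6 to 330 × 0.13 = 42.9, or about 40 to 43. That is all expected dropouts for any reason, not the number affected. The figure in Protocol Section 1.3, "cardiovascular events (5.1% brexpiprazole versus 2.9% placebo", concerns adverse events, whose counting does not depend on this row, so it does not show that a signal would be missed.

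**Conclusion.** The point holds in a limited form. The time condition does not fit a 12-week trial and rests on an undefined date. Under the baseline reading, no ET ECG before Day 84 can be flagged, and 2 of the 5 days in the Week 12 window fail. Under the consent reading, whether a Week 8 or ET ECG counts depends on screening length. The loss falls mainly on early terminators.

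The number of subjects affected would be those with a new old-infarction pattern on a disqualified last ECG. The documents give no rate from which to derive it. It is probably very small, since Protocol Section 3.4.3 excludes clinically significant ischemic heart disease. One row of a descriptive safety table and its listing is affected. Efficacy, adverse event counts and the other ECG flags are not.

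The Week 8 conclusion assumes that the pattern persists to Week 12 and that the Week 12 ECG is done on a qualifying day.

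**What to change.** For the by-arm incidence table and listing in SAP Section 9.4, count an old infarction as a finding absent at baseline and present at any on-treatment ECG, naming Week 8, ET and unscheduled recordings. This can replace the time-restricted count, or stand beside it if comparability with the existing criterion is wanted. If the restricted count is kept, define trial entry as a specific date.

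Protocol Appendix 4 carries the same condition and also guides investigators after randomization (Section 3.7.5.4). The sponsor should reconcile it with the 12-week treatment period and the ECG schedule; this review proposes no clinical criterion for it.

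The cost is one table cell and about one programming line, with no change to visits or treatment. An addendum would be enough, as SAP Addendum 2 added a safety definition in that way. The downside is that a few extra flags may reflect pre-existing infarcts or variation between readings. These would be expected to be similar in both arms.

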## 1 Introduction

This addendum to the statistical analysis plan (SAP) version 2.0 is to document a modification to the multiplicity adjustment after the approval of the original SAP (version 2.0, issued on 29 January 29, 2021) and the interim analysis plan (version 4.0, issued on September 10, 2020), and to address FDA's feedbacks on the SAP. The modification will have no impact on the familywise Type-I error rate, which is strongly controlled at a two-sided 5% level. The statistical methodology, data analysis algorithms and conventions remain the same as those in the original SAP.

## 2 Modification to the Multiplicity Adjustment

The hypotheses of interest for the planned labeling will be comprised of only the primary endpoint CMAI total score and the key secondary endpoint CGI-S score. The hypotheses pertaining to all other secondary endpoints will be excluded from the hierarchical testing procedure.

The testing will be conducted on two hypotheses of interest in the order specified below:

- 1) The primary efficacy endpoint, change from baseline to Week 12 in the CMAI total score
- 2) The key secondary efficacy endpoint, change from baseline to Week 12 in the CGI-S score

After reviewing the unblinded interim analysis results, DMC recommended that the trial be continued to the planned end. As a result, at the final analysis, the primary efficacy endpoint will be tested at a two-sided 3.5% significance level, and upon achieving significance on the primary endpoint, the key secondary endpoint will be tested at the same level. The hierarchical testing procedure controls the Type-I error rate for both the primary efficacy endpoint and the key secondary efficacy endpoint.

This page is a manifestation of an electronically captured signature

## 1 Introduction

This addendum to the statistical analysis plan (SAP) version 2.0 is to add the list of Extrapyramidal symptoms (EPS)-related adverse events (AEs) and document the changes in the Proposed List of Summary Tables after the approval of the original SAP (version 2.0, issued on 29 January 29, 2021). The addition and changes will have no impact on the familywise Type-I error rate, which is strongly controlled at a two-sided 5% level. The statistical methodology, data analysis algorithms and conventions remain the same as those in the original SAP version 2.0.

[figure not shown]
## 2 Addition of List of EPS-related AEs

[figure not shown]
EPS-related AEs are listed below and will be grouped into five categories.

[figure not shown]
- 1) Dystonic Events, which include blepharospasm, cervical spasm, clumsiness, dystonia, dystonic tremor, emprosthotonus, essential tremor, facial spasm, fumbling, gait inability, head titubation, intention tremor, Meige's syndrome, muscle contractions involuntary, muscle spasms, muscle spasticity, muscle tightness, muscle tone disorder, musculoskeletal stiffness, myotonia, nuchal rigidity, oculogyration, oesophageal spasm, opisthotonus, opisthotonus, oromandibular dystonia, oropharyngeal spasm, pharyngeal dystonia, pleurothotonus, risus sardonicus, spasmodic dysphonia, tongue spasm, torticollis, torticollis psychogenic, trismus, uvular spasm;
- 2) Parkinsonian Events, which include action tremor, akinesia, asterixis, bradykinesia, bradyphrenia, cogwheel rigidity, dysphonia, fine motor skill dysfunction, freezing phenomenon, gait disturbance, gait festinating, hypertonia, hypokinetic dysarthria, laryngeal tremor, masked facies, micrographia, mobility decreased, muscle rigidity, on and off phenomenon, parkinsonian crisis, parkinsonian gait, parkinsonian rest tremor, parkinsonism, parkinsonism hyperpyrexia syndrome, parkinsons disease, parkinson's disease, parkinson's disease psychosis, postural reflex impairment, postural tremor, propulsive gait, reduced facial expression, resting tremor, tremor, walking disability;
- 3) Akathisia Events, which include akathisia, extrapyramidal disorder, hyperkinesia, movement disorder, psychomotor hyperactivity, and restlessness;
- 4) Dyskinetic Events, which include abnormal involuntary movement scale, athetosis, ballismus, buccoglossal syndrome, chorea, choreoathetosis, chronic tic disorder, complex tic, dopamine dysregulation syndrome, drooling, dyskinesia, dyskinesia oesophageal, grimacing, motor dysfunction, muscle twitching, nodding of head, oculogyric crisis,

[figure not shown]
pharyngeal dyskinesia, protrusion tongue, provisional tic disorder, rabbit syndrome, respiratory dyskinesia, secondary tic, tardive dyskinesia, tic;

[figure not shown]
5) Residual Events, which include huntingtons disease and myoclonus.

[figure not shown]

[figure not shown]

[figure not shown]

[figure not shown]

This page is a manifestation of an electronically captured signature

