3.7.3.4 International Psychogeriatric Association

The IPA developed a provisional consensus definition of agitation utilizing *Diagnostic* and *Statistical Manual of Mental Disorders*, Fifth edition (DSM-5) terminology. The definition is intended to advance further research in agitated patients with cognitive impairment. The IPA provisional consensus definition of agitation¹⁶ is described in Table 3.7.3.4-1.

Table 3.7.3.4-1 Consensus Provisional Definition of Agitation in Cognitive Disorders									
Item									
A.									
A.	The patient meets criteria for a cognitive impairment or dementia syndrome (eg, Alzheimer's								
	disease, frontotemporal dementia, dementia with Lewy bodies, vascular dementia, other								
	dementias, a pre-dementia cognitive impairment syndrome such as mild cognitive impairment								
	or other cognitive disorder).								
	Note: Only subjects who meet the NINCDS-ADRDA criteria for Alzheimer's Disease as								
_	noted in Inclusion Criterion #3 (Section 3.4.2) are eligible for this trial.								
B.	The patient exhibits at least one of the following behaviors that are associated with observed								
	or inferred evidence of emotional distress (eg, rapid changes in mood, irritability, outbursts).								
	The behavior has been persistent or frequently recurrent for a minimum of 2 weeks' and								
	represents a change from the patient's usual behavior.								
	(a) Excessive motor activity (examples include: pacing, rocking, gesturing, pointing fingers,								
	restlessness, performing repetitious mannerisms).								
	(b) Verbal aggression (eg, yelling, speaking in an excessively loud voice, using profanity,								
	screaming, shouting).								
	(c) Physical aggression (eg, grabbing, shoving, pushing, resisting, hitting others, kicking								
	objects or people, scratching, biting, throwing objects, hitting self, slamming doors, tearing								
	things, and destroying property).								
C.	Behaviors are severe enough to produce excess disability, which in the clinician's opinion is								
	beyond that due to the cognitive impairment and including at least one of the following:								
	(a) Significant impairment in interpersonal relationships.								
	(b) Significant impairment in other aspects of social functioning.								
	(c) Significant impairment in ability to perform or participate in daily living activities.								

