5.2 Eliciting and Reporting Adverse Events

Adverse events will be recorded, starting after the ICF has been signed. The investigator will periodically assess subjects for the occurrence of AEs. To avoid bias in eliciting AEs, subjects should be asked the non-leading question: "How have you felt since your last visit?" All AEs (serious and nonserious) reported by the subject must be recorded on the source documents and eSource provided by the sponsor. All AE (including SAEs) collection is to begin after a subject has signed the ICF.

Use medical terminology in AE reporting. Adverse events should be reported as a single unifying diagnosis whenever possible or, in the absence of a unifying diagnosis, as individual signs or symptoms. Exacerbation or disease progression should be reported as an AE only if there are unusual or severe clinical features that were not present, or experienced earlier, or not expected based on the course of the condition.

In addition, the sponsor must be notified immediately by telephone, fax, or e-mail of any IREs according to the procedure outlined below, in Section 5.3. Special attention should be paid to recording hospitalization and concomitant medications.

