### 9.1 Adverse Events

All AEs will be coded by system organ class and Medical Dictionary for Regulatory Activities (MedDRA) preferred term. The incidence of the following events will be summarized by treatment group:

- Treatment-emergent AEs (TEAEs)
- TEAEs by severity
- TEAEs with an outcome of death
- Serious TEAEs
- TEAEs leading to discontinuation of the IMP

The above summaries will also be prepared for TEAEs potentially causally related to the IMP.

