## 9.6 Simpson-Angus Scale, Abnormal Involuntary Movement Scale, and Barnes Akathisia Rating Scale

The mean change from baseline to Week 12/ET in the double-blind treatment period obtained from the Simpson-Angus Scale total score, AIMS total score (total of the first 7 item scores), and BARS Global Clinical Assessment will be performed for the Safety Sample and tabulated and analyzed using ANCOVA.

The ANCOVA model will include the baseline measure and the treatment group.

The same analyses will be performed on the AIMS individual item scores 8, 9, and 10. In addition, incidence of BARS Global Clinical Assessment of Akathisia during the double-blind treatment period by severity category will be provided. Analyses of these EPS rating scales will be performed for the Safety Sample.

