### 10.3 Scales: Rules for Scoring and Handling of Missing Data

#### 10.3.1 Cohen-Mansfield Agitation Inventory

The CMAI consists of 29 items all rated on a 1 to 7 scale with 1 being the “best” rating and 7 being the “worst” rating. The CMAI total score is the sum of ratings for all 29 items. The possible total scores are from 29 to 203. The CMAI total score will be unevaluable if less than 24 of the 29 items are recorded. If 24 to 28 of the 29 items are recorded, the total score will be the mean of the recorded items multiplied by 29 and then rounded to the first decimal place.

**Factor 1:** Aggressive behavior: Hitting (including self), kicking, scratching, grabbing onto people, pushing, hurt self or other (cigarette, hot water, etc.), throwing things, cursing or verbal aggression, spitting (include at meals), tearing things or destroying property, screaming, biting.

Criteria for agitated status based on Factor 1:

- at least one aggressive behavior occurring at a frequency of at least 4; or
- at least two aggressive behavior occurring at a frequency of at least 3; or
- at least three aggressive behavior occurring at a frequency of at least 2;

**Factor 2:** Physically nonaggressive behavior: Pace, aimless wandering, trying to get to a different place, general restlessness, inappropriate dress or disrobing, handling things inappropriately, performing repetitious mannerisms.

Criteria for agitated status based on Factor 2:

- at least one physically nonaggressive behavior occurring at a frequency of at least 5; or

- at least two physically nonaggressive behavior occurring at a frequency of at least 4; or
- at least three physically nonaggressive behavior occurring at a frequency of at least 3; or
- at least four physically nonaggressive behavior occurring at a frequency of at least 2;

**Factor 3:** Verbally agitated behavior: Complaining, constant unwarranted request for attention or help, repetitious sentences or questions, negativism.

Criteria for agitated status based on Factor 3:

- at least one verbally agitated behavior occurring at a frequency of at least 5; or
- at least two verbally agitated behavior occurring at a frequency of at least 4; or
- at least three verbally agitated behavior occurring at a frequency of at least 3; or
- at least four verbally agitated behavior occurring at a frequency of at least 2;

**Factor 4:** Hiding things, hoarding things.

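### The Akathisia Events category in SAP Addendum 2 shares terms with the agitation being treated, so it and the total EPS rate can understate a drug-placebo difference

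*SAP*

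**What the plan says.** SAP Addendum 2, Section 2, sorts EPS-related adverse events into five categories. The third reads "Akathisia Events, which include akathisia, extrapyramidal disorder, hyperkinesia, movement disorder, psychomotor hyperactivity, and restlessness". The visible text gives no narrower grouping and no rule for telling restlessness that belongs to agitation from restlessness that belongs to akathisia.

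Restlessness also appears on the disease side of the plan:

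- **Entry.** Protocol Table 3.7.3.4-1 gives three qualifying behaviours. One is "Excessive motor activity (examples include: pacing, rocking, gesturing, pointing fingers", and its examples continue with "restlessness, performing repetitious mannerisms".
- **Efficacy.** SAP Section 10.3.1 builds CMAI Factor 2 from items that begin "Pace, aimless wandering, trying to get to a different place, general restlessness". These items count towards the CMAI total score, the primary endpoint.

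Psychomotor hyperactivity is named in neither place.

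Protocol Section 5.2 limits the reporting of disease symptoms: "Exacerbation or disease progression should be reported as an AE only if there are unusual or severe clinical features that were not present". It also admits features not experienced earlier or not expected from the course of the condition.

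Other information on akathisia is planned. SAP Section 9.1 states: "All AEs will be coded by system organ class and Medical Dictionary for Regulatory Activities (MedDRA) preferred term". SAP Section 9.6 analyses change in the BARS global item by ANCOVA and adds that "incidence of BARS Global Clinical Assessment of Akathisia during the double-blind treatment period by severity category will be provided". In Protocol Table 3.7-1 the row "Extrapyramidal symptoms scales (SAS, AIMS, BARS") is marked at baseline and at Week 12 or early termination only.

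**The concern.** The same behaviour can qualify a subject for entry, count in the efficacy outcome and be tallied as an extrapyramidal harm. A drug that reduces agitation could reduce reports of restlessness while causing some akathisia. The two effects then work against each other inside one category, and inside the total EPS rate.

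The total is a figure the sponsor uses to describe risk: Protocol Section 1.3 summarises the two earlier trials in this population as EPS-related TEAEs of 5.8% on brexpiprazole and 4.0% on placebo. That is a difference of 1.8 points, so a shift of one or two points from shared terms would matter to how such a figure is read. Safety and tolerability is the secondary objective. Section 1.3 describes experience in this population at doses up to 2 mg/day, whereas two-thirds of the active arm here is assigned 3 mg/day.

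**Working it through.** The documents give no rate, test or power for this category, so there is no stated figure to reproduce. The calculation below shows direction and size under assumed rates.

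**Inputs.** About 330 subjects randomised 2:1 (SAP Section 4): 330 × 2/3 = 220 on brexpiprazole and 110 on placebo. Assumed akathisia rate *a*: 1% placebo, 3% drug. Assumed background rate *b* of restlessness or hyperactivity AEs due to agitation: 3% or 5% on placebo, and equal or lower on drug. The two kinds of event are taken as independent within arm.

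**Formula.** Category rate = 1 − (1 − *a*)(1 − *b*).

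With 3% background in each arm:

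- placebo: 1 − 0.99 × 0.97 = 3.97%
- drug: 1 − 0.97 × 0.97 = 5.91%

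| Background, placebo / drug | Category, placebo | Category, drug | Difference (points) | Ratio |
|---|---|---|---|---|
| none | 1.00% | 3.00% | 2.00 | 3.0 |
| 3% / 3% | 3.97% | 5.91% | 1.94 | 1.49 |
| 3% / 1.5% | 3.97% | 4.46% | 0.49 | 1.12 |
| 3% / 1% | 3.97% | 3.97% | 0.00 | 1.00 |
| 5% / 5% | 5.95% | 7.85% | 1.90 | 1.32 |
| 5% / 3% | 5.95% | 5.91% | −0.04 | 0.99 |

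Three things follow.

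1. Equal background dilutes the ratio but hardly touches the risk difference.
2. Halving a 3% background on drug attenuates the difference without removing it: about 4.5% versus 4.0%.
3. Full masking requires the fall in agitation-related reports on drug to equal the akathisia excess, here about 2 points, or 0.02 × 220 = 4.4 subjects.

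With a larger assumed akathisia effect, 1% versus 5%, a background of 3% / 1% gives 1 − 0.99 × 0.97 = 3.97% against 1 − 0.95 × 0.99 = 5.95%. The difference is 1.98 points instead of 4.0, so about half remains.

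**Precision.** With 110 and 220 subjects and a two-sided 0.05 level, power for the akathisia term alone is about 16% for 1% versus 3% and 43% for 1% versus 5%. Reading of these rates will be descriptive whichever grouping is used.

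**Can the preferred-term tables supply the narrower rates?** For akathisia itself, yes: it is a single term. For the category without the two shared terms, or for total EPS without them, no. A subject with several terms is counted under each, so adding term counts gives only an upper limit on the number of subjects.

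**The case against.** The strongest reply is that akathisia remains visible elsewhere, and this stands. Its preferred-term rate can be read by arm, free of restlessness. AEs and concomitant medications are collected at every visit in Table 3.7-1, and Protocol Table 4.1-1 allows propranolol for akathisia or tremor, so its use leaves a record. BARS is also done at early termination, which covers subjects withdrawn because they cannot tolerate their dose. A reader might infer that the category is the only record of akathisia between BARS ratings, or that the plan cannot show whether the drug causes it. The documents support neither reading.

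Section 5.2 also keeps much ordinary agitation out of the AE data. It does not close the gap, because entry needs only one of the three behaviours: a subject enrolled for verbal aggression who later becomes markedly restless can have a reportable event in either arm.

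A broad list also has a purpose. Protocol Section 7.5.5.3 of the safety assessments (numbered 3.7.5.5.3) has BARS rate the subject's own feelings of restlessness, and with MMSE scores of 5 to 22 some akathisia may well be recorded simply as restlessness. Dropping the term altogether would lose those cases. That argues for showing both groupings.

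Finally, Section 3 of Addendum 2, an updated list of summary tables, is not in the text available. It may already contain narrower rows, so their absence cannot be asserted.

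**Conclusion.** The point holds as a minor matter of safety display. The overlap is explicit for restlessness and a matter of meaning for psychomotor hyperactivity. If the drug works on agitation, the Akathisia Events category and the total EPS rate can understate a drug-placebo difference.

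The size depends wholly on assumed rates. Equal background at 3% takes the ratio from 3.0 to 1.5 and the difference from 2.0 to 1.9 points. Complete masking needs a fall in agitation-related reports as large as the akathisia excess. A reader might take such masking as the expected result, but the documents give no background rate from which to predict it.

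Nothing here touches the primary analysis or the type I error rate.

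**What to change.** Keep the five categories. Unless the Addendum 2 table list already has them, add two subject-level rows to the EPS table as a sensitivity display:

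- Akathisia Events excluding restlessness and psychomotor hyperactivity;
- total EPS-related AEs excluding the same two terms.

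State that these rows are read beside the broad rows, the akathisia preferred term and BARS, and do not replace them.

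As a separate tidy-up, Addendum 2 lists oculogyration under Dystonic Events and oculogyric crisis under Dyskinetic Events. Putting both in one category would stop closely related reports being split by coded term; total EPS counts do not change.

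The cost is two rows from data already coded. The drawback is that two EPS rates appear where there was one, and the narrow rows miss true akathisia that was recorded as restlessness.
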